4.1. Additional assessments

4.1.1. *Exploratory Genetics: Telomere length and epigenetic biological age (optional)*

The study includes genetic sample at the screening visit that requires a separate informed consent form if the participant agrees to participate.

Exploratory genetic research studies are planned at the end of the study with the aim to evaluate the impact of FMD on telomere length used as a biomarker of individual ageing.

4.2. Prohibited Medications and Procedures

No concomitant prescription medications, over-the-counter medications, medical foods, and nutritional supplements are to be started, or doses changed during the study unless they are prescribed by the subject's primary care giver for treatment of a specific clinical event.

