3.1.2. Exclusion Criteria

- individuals who are allergic to tree nuts (macadamia, cashew, almond, pecan), soy, oats, sesame, or celery/celeriac;
- pregnant females;
- any documented cancer diagnosis within the past 5 years;
- documented myocardial infarction within past 5 years;
- documented cerebrovascular accident within past 5 years;
- chronic steroid use (longer than 45 consecutive days);
- insulin-dependent diabetes mellitus;

- individuals taking insulin or insulin-like drugs and individuals taking hypoglycemic agents other than metformin. In this last case, close attention will therefore be paid to the self-monitoring of blood glucose during the FMD cycles;
- Individuals with severe hypertension (systolic greater than 200 mmHg and or diastolic greater than 105 mmHg).

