3.1.3. Prohibited Medications, Medical Foods or Nutritional Supplements

- Change in prescription medications, over-the-counter (OTC) medications, medical foods, and nutritional supplements within 30 days prior to the start and for the duration of the study.
- Use of medications classified as narcotics 15 days prior start and for the duration of the study.
 - Use of prescription medications and/or over-the-counter medications for acute and semi-acute medical conditions 15 days prior to start and for the duration of the study. Use of acetaminophen is permitted on an as-needed basis.
 - Use of an investigational drug or participation in an investigational study within 30 days prior to the start and for the duration of the study.
 - Use of anticoagulant medications (heparin compounds or warfarin) within 30 days prior to the start and for the duration of the study. Use of aspirin 400 mg once daily is permitted
 - Subjects will not be allowed to discontinue prohibited prescription medications to meet enrolment criteria.

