7.4.5. Stopping Rules for an Individual Subject

A study subject will be discontinued from further Study Product(s) administration for:

a significant reduction of BMI greater than 15% from baseline measurement and in any case of a BMI measurement lower than 22 Kg/m² for women and 23 Kg/m² for men during the follow-up visits; any clinical adverse event, laboratory abnormality, concurrent illness, other medical condition.

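### Section 4.2 permits on-study prescriptions that 3.1.3 bars, so a glucose-lowering drug excluded at entry can be started with later FMD boxes already at home and no medication check set before a cycle

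*Protocol*

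**What the plan says.** **The bar.** Protocol 3.1.3 lists as prohibited "Change in prescription medications, over-the-counter (OTC) medications, medical foods, and nutritional supplements within 30 days prior to the start and for the duration", meaning the whole study period. It also prohibits "prescription medications and/or over-the-counter medications for acute and semi-acute medical conditions 15 days prior to start and for the duration of the study". Acetaminophen as needed and a stated daily aspirin dose are its only allowances. Section 4.3 repeats acetaminophen as rescue medication.

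**The exception.** Section 4.2 covers the same four product types as the first bullet of 3.1.3. It forbids starting them or changing their dose unless they are prescribed by the "primary care giver for treatment of a specific clinical event".

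**Entry rule for glucose-lowering drugs.** Section 3.1.2 excludes "individuals taking insulin or insulin-like drugs and individuals taking hypoglycemic agents other than metformin", and adds that "close attention will therefore be paid to the self-monitoring of blood glucose during the FMD cycles". It does not say what follows if such a drug is started after entry.

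**Product rules.** Section 7.4.5 opens "A study subject will be discontinued from further Study Product(s) administration for" and includes among its triggers "any clinical adverse event, laboratory abnormality, concurrent illness, other medical condition". Section 7.4.3 lets the study clinician reduce, hold or discontinue the food at discretion.

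**Supply and contact.** Three boxes are handed out at baseline, and those for the remaining two cycles at follow-up visit 1. Section 5.1.1 says that boxes arrive before the next cycle. Section 3.3 provides a telephone call on day 6 of each cycle, covering adverse events, compliance and dietary recall. The text for follow-up visit 1 includes current medications, but the Medications row of Table 1 has no tick there.

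**The concern.** A drug newly prescribed for an acute event is what the third bullet of 3.1.3 forbids and what 4.2 allows. Site staff have no stated way to decide which section applies, and two sites or two monitors could classify the same prescription differently.

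For most drugs this is a matter of consistent protocol compliance. For insulin and hypoglycaemics other than metformin it also bears on safety. The protocol itself treats these drugs as incompatible with entry to a study of a five-day restricted diet, and asks for attention to glucose self-monitoring in the same bullet. Metformin users may enrol, and use of glucose-lowering drugs is part of a secondary endpoint in 2.2.2, so this kind of medication is in view. If such a drug is prescribed between visits, 4.2 can be read as allowing it. The participant may then eat the next cycle from a box already at home before anyone at the site has asked about medication.

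**Working it through.** The plan states no figure to reproduce. The check is a comparison of texts, then a simple timeline.

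**1. Do 3.1.3 and 4.2 answer the same question?** Yes: both say whether a drug may be started or changed on study. Section 3.1.3 sits among the selection criteria, but its bullets run through the whole study, so it is also an on-study rule. A prescription from the primary care giver for an acute event gives *barred* under 3.1.3 and *allowed* under 4.2. Neither section refers to the other.

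**2. Do 7.4.3 and 7.4.5 resolve it?** They answer a different question, namely whether the study product continues. A drug can be allowed under 4.2 while product is stopped under 7.4.5. They therefore add no conflict, but they do not settle the drug rule either.

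**3. Would 7.4.5 catch a start of insulin or a second agent?** Usually. Such a start will normally answer a laboratory abnormality, an illness or another medical condition, all of which 7.4.5 names. Two limits remain:
- The site must know. Nothing in the text shown makes the participant report the prescription before the next cycle.
- Table 1 schedules haematological analyses, including glucose and HbA1c, at baseline and follow-up visit 2 only, and the text for visit 1 lists no blood draw. Scheduled study bloods cannot raise the laboratory trigger in between.

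**4. How long are the intervals without a medication check?** Assumptions, not stated in this form in the protocol: five evenly spaced cycles at months 0, 3, 6, 9 and 12; cycle 1 at baseline; visit 1 on day 6 of cycle 3, with current medications reviewed as its text says.
- Spacing: 365 / 4 = 91.25 days.
- Baseline to cycle 2: 91.25 / 7 = 13.0 weeks.
- Baseline to cycle 3: 2 × 91.25 = 182.5 days; 182.5 / 7 = 26.1 weeks.
- Visit 1 to cycle 4: 91.25 − 5 = 86.25 days; 86.25 / 7 = 12.3 weeks.
- Visit 1 to cycle 5: 86.25 + 91.25 = 177.5 days; 177.5 / 7 = 25.4 weeks.
- Day-6 call to the next cycle: 86.25 days, again 12.3 weeks.

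A later visit 1 shortens the intervals to cycles 4 and 5. The protocol gives no visit window, so no lower bound is offered. If staff follow Table 1 and skip medications at visit 1, the last review before cycles 4 and 5 is baseline: 3 × 91.25 / 7 = 39.1 weeks and 4 × 91.25 / 7 = 52.1 weeks.

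**5. How many boxes can be at home?** After cycle 1, 3 − 1 = 2 unused boxes. After visit 1, the two for the remaining cycles. So up to two.

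**The case against.** The strongest reply is that the product rules already cover the dangerous case. Section 4.2 permits a start only for a specific clinical event, and 7.4.5 then requires discontinuation for almost any such event. Ordinary escalation with no specific event is not permitted by 4.2 at all. The rule in 7.1 that expected worsening of a pre-existing condition is not an adverse event does not defeat this, because 7.4.5 separately names laboratory abnormality, illness and other conditions. This largely stands. What it leaves open is timing: both product rules work only once the site knows.

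On supply, 5.1.1 can be read as issue cycle by cycle, which would shrink the problem. The baseline and visit 1 texts point to batches. On contact, 7.3.4 and 7.4.1 require adverse-event questioning at each contact, 8.4 foresees medication logs and data from calls and diaries, and Appendices A to C, not shown, may ask about drugs. None of the text shown places a check before a cycle. Glucose self-monitoring helps, but only after the cycle has begun.

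Four stronger readings are tempting, and the protocol does not support them:
- A reader might infer that 3.1.3, 4.2, 7.4.3 and 7.4.5 are four competing rules. Only the first two conflict; the others govern product.
- A reader might extend the safety concern to anticoagulants, because 3.1.3 bars "Use of anticoagulant medications (heparin compounds or warfarin) within 30 days prior to the start and for the duration of the study", or to narcotics and chronic steroids. The protocol gives no safety reason for those bars in relation to FMD cycles. For drugs barred on study by 3.1.3, only the textual contradiction applies.
- A reader might take the intervals as a measure of risk. They show opportunity only.
- A reader might take the endpoint in 2.2.2 as expecting new insulin starts. It speaks of reduction or stabilisation of use.

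**Conclusion.** The contradiction between 3.1.3 and 4.2 is certain on the text. The safety consequence is real but narrow. It concerns insulin and hypoglycaemics other than metformin, prescribed between visits, where the site does not hear of it before the participant eats a cycle from a box already at home. Existing rules would usually stop or hold product once the site is aware.

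Its size cannot be given in participants, because the protocol states neither the number of metformin users nor a rate of drug starts. The intervals of roughly 12 to 26 weeks from the last scheduled medication review rest on evenly spaced cycles, batch issue of boxes, and a medication review at visit 1. No effect on the primary endpoint or its analysis is claimed. The change is worth making because it is cheap and acts before a cycle rather than during it. Confidence is moderate, since the appendices that define the calls are not shown.

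**What to change.** 1. In 3.1.3, state that on-study changes are governed by 4.2, in addition to the existing acetaminophen and aspirin allowances.
2. In 4.2, add that a participant who starts insulin or a hypoglycaemic other than metformin must contact the site before the next FMD cycle, and that further cycles are held until the study clinician clears them. State that 7.4.5 still governs the underlying event and that the T1 and T2 assessments continue, so that endpoint data are kept.
3. Print this instruction with each box, and add a medication question to the existing day-6 call. The call alone is not enough, since it follows the diet days and precedes the next cycle by about 12 weeks. The printed instruction is what acts before the cycle.
4. Tick Medications at follow-up visit 1 in Table 1, to match the visit text.

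**Cost.** A few sentences, one question in calls already planned, one table entry, and at most 5 × 267 = 1,335 printed slips, taking the maximum of 267 subjects from section 8.1. No scheduled visits or calls are added, but the site will handle occasional extra participant contacts and clearances. A few held participants may complete fewer than five cycles.

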4.3. Rescue Medications

Acetaminophen, may however, be used for mild headache or myalgia at a dose of 650 mg three times daily as needed.

4.4. Subject Compensation

Subjects will not be compensated for participation in this trial.

5. Study Product:

Formulation, Packaging, Labelling, Preparation, Administration, and Dosage of Study Products

The subjects will be instructed to follow their usual diet plan, except for the 5 days when they will be eating the foods included in the FMD box. The FMD diet is made up of nut bars, dehydrated soups, tea, olives, kale crackers, electrolyte beverages, and a chocolate crisp bar.

- Nut bars: Almond, macadamia nuts, pecans, vegetable inulin fibre (chicory root fiber), honey, coconut flour, flaxseed, natural flavour, sea salt, rosemary extract.
- Almond and Kale crackers: almonds, sesame seeds, tapioca flour, chia seeds, golden flax seeds, sunflower seeds oil, kale, sea salt, coconut sugar, coconut vinegar, onion powder, chili pepper, cumin seeds, black pepper, antioxidant: extract rich in tocopherol, garlic, origan, acidifier: citric acid.

- Electrolyte beverages containing water, natural vegetable glycerine, natural flavour,
- Olives.
- Spearmint tea, spearmint lemon tea, hibiscus tea.
- There are 5 different soups, which contain various combinations of rice flour, rice starch, potato flakes, tomato concentrate, sweet red pepper, basil, onion, leek, extra virgin olive oil, parsley, peas, yeast extract, savoy cabbage, carrot, garlic, spinach, celery, turmeric, black and white beans, champignon mushroom powder: minestrone, mushroom, tomato, vegetable, black beans soup;
- Chocolate crisp bar: inulin, almond butter, brown rice, cocoa powder, almonds, chocolate chips (brown sugar, cocoa mass, cocoa butter), rolled oats, brown rice syrup, flaxseed oil, rice dextrin, grape juice, salt.

To evaluate the adherence to the FMD and its metabolic effects, patients will receive ketone test strips together with each FMD kit to self-monitor urinary ketone bodies.

5.1.1. Study Product Storage and Stability

Subjects will receive the FMD boxes before the start of the next FMD cycle. The study products will be handled and dispensed to subjects at room temperature at the study site, according to good clinical practices.

5.1.2. Study Product Accountability Procedures

It is the responsibility of the PI to ensure that a current record of study product disposition is maintained at the Study Site, and that records and logs include:

- amount of study products received and placed in storage area;
- dates and initials of individual responsible for investigational product inventory entry/movement;
- amount dispensed to and returned by each subject, including unique subject identifiers;
- amount transferred to another area for dispensing or storage;
- non-study disposition (e.g. lost, broken, wasted);
- amount destroyed at the site (if applicable).

The unused study products for this study will be disposed off according to good clinical practices.

5.1.3. Potential Risks

There is a possibility, however, that a subject could be sensitive to food ingredients in one or more of the food formulas and have an allergic or intolerance reaction. Potentially serious reactions may include face and throat swelling, trouble breathing, anaphylaxis (shock), convulsions, and death.

5.1.4. Potential Benefits

The FMD is designed to achieve the beneficial effects of fasting while providing micronutrient nourishment (vitamins, minerals and others) from which the body is deprived during fasting. It minimizes the psychological burden of pure fasting. The subjects will receive extensive medical testing

and these results will be available to the subjects after completion of their participation for their ongoing care.

5.1.5. Assessment of Subject Compliance with Study Product

Compliance will be measured using both a subject calendar provided by the investigator and direct verification of consumption of the FMD. Subjects will not be asked to return FMD boxes.

6. Description of Specific Testing Modalities

6.1. Hematological analyses

Complete metabolic and lipid panels (after overnight fasting) will be completed at the Istituto Clinico “[name]. R. De Blasi” srl, [name], in Reggio Calabria and analyzed immediately after the blood draw of each visit. Clinical and biochemical evaluations include lipid profile (total cholesterol, LDL-cholesterol, HDL-cholesterol and triglycerides), serum/plasma, albumin, alkaline phosphatase, insulin-like growth factor 1 (IGF-1), Insulin-like growth factor-binding protein 1 (IGFBP1), insulin, C-reactive protein (CRP), aspartate aminotransferase (AST), alanine aminotransferase (ALT), homocysteine, glucose, glycosylated hemoglobin (HbA1c).

6.2. Blood collection and storage

Blood samples will be collected and stored for future biomarker analyses. In particular, two 6.0 ml ethylenediaminetetraacetic acid tube of whole blood samples will be collected for each participant. One tube will be spun at 1300 g for 20 minutes at room temperature to generate supernatant (plasma), buffy coat and red blood cells which will be individually aliquoted into 1 ml, polypropylene, cryovials and stored at -80 °C for later analysis. The other 6.0 ml tube of whole blood will individually aliquoted into 1 ml and stored at -80 °C for later analysis as previously mentioned.

6.3. Blood Pressure Measurements

Subjects will not consume any caffeine or alcohol or use tobacco products within 6 hours of the blood pressure measurement. Subjects will have their blood pressure on each visit. Subject's blood pressure will be measured in the left arm sitting position three times at 2-minute intervals following the American Heart Association (AHA) guidelines for blood pressure measurement. Heart rate will be measured with each blood pressure measurement.

6.4. Body Impedance Analysis

The BIA technique is based on the fact that lean tissues have a high water and electrolyte content, and thus provide a good electrical pathway. Fat contains a lower percentage of body water, and thus is a poor conductor of the electrical signal. Utilizing a low energy, high frequency, electrical signal (50 kHz, 500 micro amp), a measurement of the baseline resistance and reactance to the flow of electrical current can be made. The measurement relates directly to the volume of the conductor, which is used to determine total body water, lean body mass, and finally, fat mass and percent body fat measurement on the Tanita® scale.

6.5. Telomere length (optional)

Telomere length will be measured in genomic DNA extracted from stored buffy coat samples by quantitative polymerase chain reaction (qPCR) using a method adapted from the one originally

described by Cawthon (2009). Telomere length will be performed on the blood samples collected before the dietary intervention and at the end of the treatment. Telomere length measurements will be carried out at the laboratory of Genetics of Department of Biology, Ecology and Earth Sciences, University of Calabria or at the University of Palermo.

Epig. Clock could also be evaluated.

6.6. Clinical and Research Laboratory Evaluations and Specimen Collection

6.6.1. Biohazard Containment

As the transmission of HIV and other blood-borne pathogens can occur through contact with contaminated needles, blood, and blood products; appropriate blood and secretion precautions will be employed by all personnel in the drawing of blood and shipping and handling of all specimens for this study, as currently recommended by the Centers for Disease Control and Prevention and the National Institutes of Health. The samples will be collected by specialized personnel.

7. Safety

7.1. Definition of an adverse event (AE)

An AE is any unanticipated or unintended medical occurrence or worsening of a sign or symptom (including an abnormal laboratory finding) or disease in a study subject, including those events which do not necessarily have a causal relationship with the study condition, procedures or Study Product(s), that occurs after the informed consent is obtained.

Pre-existing conditions or illnesses which are expected to exacerbate or worsen are not considered adverse events and will be accounted for in the subject's medical history.

7.2. Definition of a serious adverse event (SAE)

A SAE is defined as an AE meeting one of the following outcomes:

- Death during the period of protocol defined surveillance.
- Life Threatening Event (defined as a subject at immediate risk of death at the time of the event).
- Inpatient hospitalization or prolongation of existing hospitalization during the period of protocol defined surveillance.
- A congenital anomaly or birth defect
- A persistent or significant disability/incapacity.
- Any other important medical event that may not result in one of the above outcomes, may be considered a serious adverse event when, based upon appropriate medical judgment, the event may jeopardize the subject and may require medical or surgical intervention to prevent one of the outcomes listed above. Examples of such medical events include allergic bronchospasm requiring intensive treatment in an emergency room or at home, blood dyscrasias or convulsions that do not result in inpatient hospitalization, or the development of drug dependency or drug abuse.

7.3. Assessing, Recording, Analyzing, and Managing Safety Parameters

7.3.1. Methods and Timing for Assessment

Adverse or clinical events will be assessed at each clinical visit. Each visit is conducted by a clinician. All reported events will be recorded in the subject's medical record.

7.3.2. AE Severity—Grading Scale

Each adverse event will be graded for severity. All laboratory and clinical AEs that occur in a subject, will be assessed for severity and classified into one the categories below following a standard criterion of Mild, Moderate or Severe.

- Mild Adverse Event — event requires minimal or no treatment and does not interfere with the subject's daily activities.
- Moderate Adverse Event — event results in a low level of inconvenience or concern with the therapeutic measures. Moderate events may cause some interference with functioning.
- Severe Adverse Event — event interrupts a subject's usual daily activity and may require systemic drug therapy or other treatment. Severe events are usually incapacitating.

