- Any sound medical, psychiatric and/or social reason which, in the opinion of the PI, would preclude safe participation in this study or interfere with compliance.
- Abnormal laboratory findings including: abnormal blood counts (haematocrit < 33% or > 47%; WBC < 3.0 or > 12.0 $\times 10^3/\text{mm}^3$; platelets < 140 or > 500 $\times 10^9/\text{L}$); abnormal kidney function test (creatinine > 2.5 mg/dL) or liver function test(s) (AST, ALT, alkaline phosphatase) > 1.5X the upper limit of normal; serum calcium > 11 mg/dL; serum K < 3.5 mEq/L; Na < 134 or > 148 mmolL⁻¹

3.1.8. *Women of Childbearing Potential*

Contraception: the effects of the study products on the developing human fetus have not been studied extensively. For this reason, women of childbearing potential must agree to use adequate contraception (hormonal or barrier method of birth control; abstinence) prior to study entry and for the duration of study participation. Females of childbearing potential will have a pregnancy test prior to receiving study products. Should a woman become pregnant or suspect she is pregnant while participating in this study, she should inform study staff and her primary care physician immediately.

Pregnancy: because there is an unknown but potential risk for adverse events in pregnant women during treatment with the study products, pregnant women are not eligible for study participation.

Breast-feeding: Because there is an unknown but potential risk for adverse events in nursing infants secondary to treatment of the mother with the study products, breastfeeding mothers are not eligible for study participation.

3.2. *Recruitment*

The participants will be identified within the intervention groups of the previous clinical studies (*Studio degli effetti della dieta mima-digiuno e della dieta della longevità sulla composizione corporea, fattori di rischio per malattie età-correlate e marcatori dell'invecchiamento in uno studio randomizzato 1 and 2*) who are willing to start a new study for other 12 months, and who completed the study less than 6 months prior to starting the new study and achieved the study's objectives. Blood tests and a nutritional assessment will be conducted, serving as the baseline for the new study. The recruitment period will last up to 3 years

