7.4.4. Halting Rules for the Protocol

The PI will closely monitor and analyze study data as it becomes available and will make determinations regarding the presence and grading of adverse events. Evaluation of adverse events will be analyzed for the study products and with regard to the known complications associated with administration. The study will be halted (no new enrollments and no further administration of product) by the investigators and a report will be submitted to the IRB (if applicable) if a safety issue is identified.

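### Section 7.3.2 grades laboratory adverse events without using the measured value, so their recorded severity does not reflect the size of the deviation

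*Protocol*

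**What the plan says.** Protocol 7.1 brings laboratory results into the adverse event definition, which covers "worsening of a sign or symptom (including an abnormal laboratory finding" and the like. Section 7.3.2 then uses a single severity scale: "All laboratory and clinical AEs that occur in a subject, will be assessed for severity and classified into one the categories below". Its three levels are:

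- Mild: "event requires minimal or no treatment and does not interfere with the subject's daily activities".
- Moderate: "event results in a low level of inconvenience or concern with the therapeutic measures. Moderate events may cause some interference with functioning".
- Severe: the event interrupts the subject's "usual daily activity and may require systemic drug therapy or other treatment. Severe events are usually incapacitating".

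Section 7.3.2 refers to a standard criterion but does not identify it, and no laboratory toxicity scale is named elsewhere in the protocol. Numeric laboratory limits do appear in 3.1.7, for example "liver function test(s) (AST, ALT, alkaline phosphatase) > 1.5X the upper limit of normal" and creatinine above 2.5 mg/dL, but only as reasons for exclusion at entry.

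Under 7.3.4, each reportable event is recorded with its start date, stop date, severity and relationship to the product. In 7.4.4 the PI "will make determinations regarding the presence and grading of adverse events".

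**The concern.** A severity grade should separate small events from large ones. Many laboratory abnormalities, such as raised liver enzymes or creatinine, cause no symptoms and may lead to no treatment. For these, a scale built on function and treatment cannot tell a trivial deviation from a marked one.

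Severity is the only one of the four descriptors in 7.3.4 that says how bad an event is. Section 7.4.1 counts haematological, chemical and immunologic monitoring as part of the safety assessment. If the grade carries no information about size, anyone relying on recorded severity for a laboratory event would have to go back to the laboratory report. This is not detail left to an analysis plan, because the protocol itself fixes the scale and expressly applies it to laboratory events.

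**Working it through.** No sample size, error rate or event count is involved. The check applies the three definitions in 7.3.2, as written, to laboratory events without symptoms. The multiples of the upper limit are illustrative; 1.5 times and 2.5 mg/dL are the entry limits in 3.1.7.

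**Step 1: what each grade requires.** Mild has two joint conditions: minimal or no treatment, and no interference with daily activities. Moderate requires a low level of inconvenience, or concern with the therapeutic measures; interference is optional. Severe requires interruption of usual daily activity; treatment is optional.

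**Step 2: apply them to symptom-free findings.**

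| Finding, no symptoms | Treatment | Both Mild conditions met? | Severe condition met? | Grade as written |
|---|---|---|---|---|
| ALT just above the upper limit | minimal or none | yes | no | Mild |
| ALT 1.6 times the upper limit | minimal or none | yes | no | Mild |
| ALT 10 times the upper limit | minimal or none | yes | no | Mild |
| Creatinine above 2.5 mg/dL | minimal or none | yes | no | Mild |
| Any of these | more than minimal | no | no | Moderate is the nearest fit |

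The first four rows differ widely in size and share one grade. Only treatment moves the grade, in the last row. Size alone never does.

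**Step 3: where the grade is used.**

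- Event record (7.3.4): severity is recorded.
- PI review (7.4.4): grading is part of it, but the study is halted when a safety issue is identified, with no grade threshold.
- Serious adverse events (7.2): decided by outcome or medical judgment, with blood dyscrasias among the examples; no dependence on grade.
- Individual stopping (7.4.5): names laboratory abnormality without a severity level.
- Safety evaluation (8.6.3): adverse events are reviewed for occurrence, and CMP and CBC data are tallied separately; no summary by severity is planned.

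**Step 4: when it can matter.** Table 1 schedules post-baseline blood analyses only at follow-up visit 2, at 12 months and after the fifth diet cycle. A grade given then cannot change that participant's exposure. Recruitment may last up to 3 years (3.2), however. If it runs the full period, the first participants' 12-month results arrive with up to 36 − 12 = 24 months of recruitment remaining, so they can inform decisions about later participants.

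**The case against.** The strongest reply is that a functional mild/moderate/severe scale is coherent, that no stopping, halting, serious-event or endpoint rule depends on the grade, and that the laboratory reports are source documents (7.3.4), so the values are kept. Tabulating values by band is also commonly left to an analysis plan. All of this stands as a limit on the consequences. It does not remove the defect, because the recorded grade for laboratory events remains uninformative about size by the protocol's own rule.

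A reader might infer four stronger points that the document does not support.

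- That every silent abnormality is Mild. Mild also depends on treatment, so one needing more than minimal treatment is not Mild. The Moderate wording on inconvenience or concern also gives the clinician some latitude, for instance where product is reduced or held under 7.4.3. That wording is still not a criterion of size.
- That laboratory events will appear as almost all mild. The protocol gives no rate of asymptomatic, untreated abnormalities, and 8.6.3 plans no table by severity.
- That safety oversight turns on these grades. In 7.4.4 grading is something the PI determines, not a threshold that triggers a halt.
- That 7.3.2 contradicts 3.1.7. Entry limits and severity bands serve different purposes. The 3.1.7 list has no glucose value, and it includes calcium, sodium and potassium, which the Table 1 footnote does not itemise.

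**Conclusion.** The point holds in a limited form. Under 7.3.2 an asymptomatic laboratory abnormality needing minimal or no treatment is Mild at any value, and no asymptomatic abnormality meets the Severe definition. The recorded severity of laboratory events therefore does not reflect the size of the deviation.

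The reach is modest: the severity entry, the PI's review of grades and any reporting by severity, with scheduled results arising only at 12 months. It is worth correcting because the change is cheap and early results can bear on later participants.

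The conclusion assumes that the definitions are applied as worded, that the interruption in the Severe grade comes from the event itself, and that the unidentified standard criterion contains no laboratory scale. If it does contain one, naming it would settle the matter.

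**What to change.** In 7.3.2, keep the functional scale for clinical adverse events. Grade laboratory adverse events by the size of the deviation, on a value-based laboratory scale chosen by the sponsor, or identify the standard criterion if it already includes such a scale. The scale should cover the analytes actually measured after baseline. The 3.1.7 entry limits need not serve as its bands. In 8.6.3, report laboratory adverse events by that grade alongside the CMP and CBC tally.

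The cost is a short table and a grade programmed from laboratory values. Some laboratory events will carry a higher grade than under the present wording. Serious-event classification and individual stopping need no change for this purpose.
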